# 9.7.1.1. Primary Objective 1: Demographics, comorbidities, and prior and current medicationsmm,nn

The proportion of patients treated with tofacitinib without evidence of an approved indication will be described and tabulated.

The demographic variables listed in Table 3 will be described and tabulated.

The comorbidity and medication variables listed in Table 3 will be described and tabulated for each patient's overall study period and stratified by whether they occurred prior to and/or after the index tofacitinib dispensing (as applicable) and by age (e.g., <65 and 65 years and older). They may also be additionally stratified by sex.

<sup>mm In GKV claims, outpatient diagnoses are reported quarterly.

<sup>nn The data sources are unable to reliably ascertain severity of hepatic impairment and renal impairment.

# 9.7.1.2. Primary Objective 2: Prescribers' adherence to the tofacitinib aRMMsoo,pp

# 9.7.1.2.1. Compliance to the recommended posology per indication and duration of use

Average daily dose, as listed in Table 3 and defined in Section 9.3.4, will be reported for each of the pre-specified time intervals as a continuous and categorical variable and stratified by approved indication group ("RA and PsA" or "UC"), age (e.g., <65 and  $\geq$ 65 years), presence of  $\geq$ 1 VTE risk factor in the 12 months prior to tofacitinib initiation, prior use of an alternative therapy (i.e., biologic) in the 12 months prior to tofacitinib initiation; and reporting period;qq it may additionally be stratified by sex.

Duration of tofacitinib therapy, as listed in Table 3 and defined in Section 9.3.3, will also be described, tabulated, and stratified by age (e.g., <65 and  $\geq 65$  years); it may additionally be stratified by sex.

The variables listed under 'Outcome: Compliance to recommended posology' in Table 3 will be described and tabulated.

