# 7. RATIONALE AND BACKGROUND

Tofacitinib citrate (Xeljanz®) is an oral Janus kinase inhibitor approved by the European Commission (EC) in March 2017 as an immediate-release film-coated tablet (5 mg), taken twice daily (BID), for the treatment of adults with moderate-to-severe active rheumatoid arthritis (RA) who have had inadequate response or intolerance to one or more disease-modifying antirheumatic drugs (DMARDs). The EC subsequently approved a prolonged-release film-coated tablet (11 mg), taken once daily (QD), in December 2019. RA is a chronic systemic autoimmune disease characterized by inflammation and progressive destruction of joints. Despite a number of treatment options available, many patients do not sustain remission. In clinical trials, patients treated with 5 mg of tofacitinib BID, in combination with methotrexate (MTX), showed significantly reduced disease activity scores and improved physical functioning and general health status as compared to patients on placebo. The approved dose of tofacitinib for the treatment of moderate-to-severe active RA is 5 mg BID or prolonged-release 11 mg QD, which should not be exceeded, in combination with MTX; it may also be given as monotherapy in the case of intolerance to MTX or when treatment with MTX is inappropriate.

In June 2018, tofacitinib 5-mg tablet (immediate-release) was approved by the EC, in combination with MTX, for the treatment of active psoriatic arthritis (PsA) in adults with inadequate response or intolerance to a prior DMARD therapy. PsA is an inflammatory arthritis occurring in between 6%-42% of patients with psoriasis. In clinical trials, patients treated with 5 mg of tofacitinib BID, in combination with a non-biologic DMARD, achieved significantly improved clinical response and physical functioning over the 6- and 12-month study periods. The approved dose of tofacitinib for the treatment of active PsA is 5 mg BID, which should not be exceeded.

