Finally, in July 2018, tofacitinib 5-mg tablet and 10-mg tablet (immediate release) were approved by the EC for the treatment of moderately-to-severely active ulcerative colitis (UC) in patients with an inadequate response, a loss of response, or an intolerance to conventional therapy or a biologic agent. UC is a bowel disease characterized by inflammation and ulcers in the colon and rectum. In clinical trials, patients treated with 5 mg or 10 mg of tofacitinib BID were more likely to achieve and/or maintain a clinical response and remission of their condition as compared to patients in the placebo group. At the time of initial approval, the doses of tofacitinib for the treatment of moderately-to-severely active UC were 10 mg BID for induction (up to a 16-week period) and 5 mg BID for maintenance, which should not be exceeded.

The following table summarizes the date tofacitinib was approved by the EC and the approved dose for each of the 3 approved indications as of June 2021.

Indication	Date approved by the EC	Approved dose
RA	March 2017	5 mg immediate-release tablets BID
	December 2019	11 mg prolonged release tablets QD
PsA	June 2018	5 mg immediate-release tablets BID
UC	July 2018	5 mg or 10 mg immediate-release tablets BID

Table 1.	Summary of appro	oved indications and	dosages for tofacitinib
----------	------------------	----------------------	-------------------------

Abbreviations: EC = European Commission; PsA = psoriatic arthritis; RA = rheumatoid arthritis; UC = ulcerative colitis.

**Note:** BID is an abbreviation for "bis in die," which in Latin means twice a day; QD is an abbreviation for "quaque die," which in Latin means once a day.

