### 8. RESEARCH QUESTION AND OBJECTIVES

The research question is: Is there evidence that prescribers in the EU are compliant with the recommendations and limitations for use described in the tofacitinib aRMM materials?

The primary objectives are to:

- 1. Describe the characteristics of patients treated with tofacitinib, stratified by study country (i.e., Sweden, Hungary, the Netherlands, and Germany) and indication (i.e., RA, PsA, and UC; off-label indications), in terms of:
  - Demographics (e.g., age, sex); and
  - Comorbidities and prior and current medication use.

<sup>b The 2021 signal evaluation procedure also required the evaluation of tofacitinib use in elderly patients aged  $\geq$ 65 years, however, this assessment had already been added to the protocol following the findings from the 2019 Article 20 referral.

- 2. Evaluate prescribers' adherence to the tofacitinib aRMMs, specifically:
  - Compliance to the recommended posology per indication (average daily dose [ADD]) and duration of use;
  - Compliance to patient screening and laboratory monitoring prior to and during tofacitinib treatment; and
  - Compliance to recommendations for limitations of use, including:
    - Use in patients with VTE risk factors;
    - Use in patients aged 65 years and older;
    - Use in patients with CV risk factors;
    - Use in patients with malignancy risk factors;
    - Contraindicated use; and
    - Use with concomitant medications not compatible with tofacitinib.

The secondary objectives are to:

- 1. Describe prescribing patterns over time; and
- 2. Describe changes in the utilisation of tofacitinib following the updated recommendations and limitations for use implemented after the 2019 Article 20 referral and the 2021 signal evaluation procedure, specifically:
  - Use in patients with VTE risk factors;
  - Use in the elderly (patients aged 65 years and older);
  - Use in patients with CV risk factors; and
  - Use in patients with malignancy risk factors.

**Note:** In Gesetzliche Krankenversicherung (GKV) claims (Germany), outpatient diagnoses are reported quarterly, which could result in the misclassification of baseline clinical characteristics and select outcomes of interest, impacting all objectives except for primary objective 2.

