# 9. RESEARCH METHODS

## 9.1. Study design

This will be a descriptive drug utilisation study using secondary data collected from databases in Sweden, Hungary, the Netherlands, and Germany. These databases will be used to identify patients who are tofacitinib users and obtain data on patient demographics, diagnoses, prescription medication dispensings, procedures, and administered screening and monitoring tests. All results will be stratified by country and approved indication (i.e., RA, PsA, and UC), unless otherwise specified. Additionally, the proportion of patients treated with tofacitinib without evidence of an approved indication will be described and tabulated, stratified by study country.

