## 9.3. Variables

### 9.3.1. Outcomes

The primary outcomes of interest will be (see Table 3 for operational definitions):

- The demographics, comorbidities, and prior and current medications (including prior use of biologics) of tofacitinib patients;d,e
- Prescribers' adherence to the tofacitinib aRMMs, specifically:
  - Compliance to the recommended posology per indication and duration of use, as measured by:f
    - ADD of tofacitinib therapy, calculated in 8-week intervals from Week 0 through Week 47, and reported in the following categories:
      - Up to 5 mg ADD;
      - >5 to 11 mg ADD;

<sup>c This exclusion criterion will primarily apply to those patients who received their index tofacitinib prescription for an indication within the first 3 months after approval of that indication.

<sup>d The data sources are unable to reliably ascertain severity of hepatic impairment and renal impairment.

<sup>e In GKV claims, outpatient diagnoses are reported quarterly.

<sup>f The study outcomes that contain an ADD component will *not* be assessed in Hungary or the Netherlands. The Hungarian administrative claims database is unable to estimate ADD, either directly or by proxy, due to how tofacitinib is captured in the database. In the high-budget impact medication dataset of the PHARMO Database Network (Netherlands), neither ADD nor the number of pills per prescription is captured.

- >11 to 15 mg ADD;
- >15 to 20 mg ADD; and
- >20 mg ADD;

Note that within these reporting intervals and categories, ADD will also be reported by approved indication or by the indication groups: "PsA or RA" and "UC", presence of  $\geq$ 1 VTE risk factor prior to tofacitinib initiation, and prior use of an alternative therapy (i.e., biologic) in the 12 months prior to tofacitinib initiation; depending on the objective, outcomes will be stratified by reporting period;e,g

- The proportion of patients with an ADD of >11 mg during any of the 8-week follow-up intervals and no evidence of a diagnosis for UC; and
- The proportion of patients with an ADD of ≥15 mg in Weeks 16-23, Weeks 24-31, Weeks 32-39, and/or Weeks 40-47 of follow-up with evidence of a diagnosis for UC but no use of an alternative therapy (i.e., biologic) *prior to* tofacitinib initiation;

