Average daily dose (ADD) t	Outcome: Compliance to recommended posology	Defined in Section 9.3.4. Assessed during the follow-up period.	
A patient with an ADD of >11 mg during any of the 8-week follow-up intervals and no evidence of a diagnosis for UC t	Outcome: Compliance to recommended posology	Defined as 0 ICD-10 diagnosis codes for UC prior to and including the date of the first tofacitinib prescription dispensing in an 8-week follow-up interval that has an ADD of >11 mg (ADD defined in Section 9.3.4).	

1 able 5. Operational definitions of study variables in the selected databas	Table 3.	Operational definitions of stud	y variables in	the selected	database
--	----------	--	----------------	--------------	----------

<sup>s In GKV claims, outpatient diagnoses are reported quarterly.

<sup>t The study outcomes that contain an ADD component will *not* be assessed in Hungary or the Netherlands. The Hungarian administrative claims database is unable to estimate ADD, either directly or by proxy, due to how tofacitinib is captured in the database. In the high-budget impact medication dataset of the PHARMO Database Network, neither ADD nor the number of pills per prescription is captured.

Variable	Role	Operational definition	
A patient with an ADD of $\geq$ 15 mg in Weeks 16-23, Weeks 24-31, Weeks 32- 39, and/or Weeks 40-47 of follow-up with evidence of a diagnosis for UC but no use of an alternative therapy (i.e., biologic) prior to tofacitinib initiation t	Outcome: Compliance to recommended posology	Defined as ≥1 ICD-10 diagnosis codes for UC and ≥1 prescription dispensing for a biologic (as identified by ATC codes) prior to and including the date of the index tofacitinib prescription with an ADD ≥15 mg in Weeks 16-23, Weeks 24-31, Weeks 32-39, and/or Weeks 40- 47 of follow-up (ADD defined in Section 9.3.4). Complete list of biologics in ANNEX 6. LIST OF ATC CODES FOR MEDICATIONS OF INTEREST TO AVOID WHILE TAKING TOFACITINIB. Note: This definition will miss those who have 1 10-mg BID prescription and the remaining prescriptions are 5-mg BID.	
Compliance to patient screening and laboratory monitoring prior to and during tofacitinib treatment u			

 Table 3.
 Operational definitions of study variables in the selected databases

The following recommended screenings and monitoring will be assessed in the following timeframes:

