#### 9.7.1. Primary analysis

The primary analyses will be conducted per approved indication per country, unless otherwise specified. Data will *not* be pooled across countries due to heterogeneity in: how the data are recorded in each database, local data protection laws, and prescribing and coding practices.

Results will be provided as descriptive statistics; no comparative statistical analyses will be conducted. Categorical variables will be reported using frequency distributions. Ordinal variables will be reported using frequency distributions, means, standard deviations (SDs), minimums, 25th percentiles, medians, 75th percentiles, and maximums, unless otherwise specified. Continuous variables will be reported using means, SDs, minimums, 25th percentiles, medians, 75th percentiles, and maximums, unless otherwise specified. When relevant, 95% CIs will be calculated for the study outcomes outlined in Section 9.3.1 (Outcomes) and Table 3.

Missing values will be reported as missing and no imputation will be undertaken. Results will be summarized in tables and figures in Microsoft® Excel and/or Word format.

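### The average-daily-dose measures do not apply the PsA dose limit that the protocol states: one 11 mg prolonged-release tablet daily passes as compliant in PsA

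*Protocol*

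**What the plan says.** Section 8 sets as part of primary objective 2: "Compliance to the recommended posology per indication (average daily dose [ADD]) and duration of use". Section 7 gives the limits. For PsA: "The approved dose of tofacitinib for the treatment of active PsA is 5 mg BID, which should not be exceeded". Table 1, which states approved doses as of June 2021, lists "11 mg prolonged release tablets QD" under RA only, with approval in December 2019.

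The measures are fixed in three places.

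- **Flag.** For patients without UC, Sections 9.3.1 and 9.3.2 (Table 3) define one posology outcome: "A patient with an ADD of >11 mg during any of the 8-week follow-up intervals and no evidence of a diagnosis for UC".
- **Bands.** Sections 9.3.1 and 9.3.4 use the same ADD categories. One runs from above 5 mg to 11 mg and the next starts above 11 mg.
- **Strata.** Section 9.1 says: "All results will be stratified by country and approved indication (i.e., RA, PsA, and UC), unless otherwise specified". Section 9.7.1 says: "The primary analyses will be conducted per approved indication per country, unless otherwise specified". For ADD, Section 9.3.1 leaves a choice: "ADD will also be reported by approved indication or by the indication groups", and Section 9.3.4 offers the same choice. Section 9.7.1.2.1 then takes the grouped form: "stratified by approved indication group ('RA and PsA' or 'UC". It reports ADD both as a continuous and as a categorical variable.

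ADD is not assessed in Hungary or the Netherlands. Section 9.3.4 leaves the exact ADD definition for each database to the SAP.

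**The concern.** A per-indication compliance objective should apply each indication's own limit. RA has two approved regimens, at 10 and 11 mg/day. PsA has one, at 10 mg/day. The flag and the band are both set at the RA ceiling and applied to PsA as well. A PsA patient on the 11 mg tablet is therefore not flagged and falls in the same category as a PsA patient on the approved regimen.

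The continuous ADD summary could still have shown values near 11 mg in PsA. In a pooled RA and PsA stratum it cannot, because 11 mg is an approved RA dose. No listed outcome would then show PsA use of a formulation that the protocol describes as approved for RA only, and the study report would be silent on one departure from posology that its primary objective covers.

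**Working it through.** **Inputs.** PsA limit and RA regimens: Section 7 and Table 1. Bands: Sections 9.3.1 and 9.3.4. Flag: Section 9.3.1 and Table 3. Indexing period of 81 months, April 2017 to December 2023: Section 9.2.1. The protocol gives no figure of its own for this point to reproduce.

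**Step 1: place each regimen in the stated rules, at its nominal daily dose.**

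| Regimen | mg/day | Band | Flag (>11 mg) | Above PsA limit (10 mg)? |
|---|---|---|---|---|
| 5 mg twice daily | 2 × 5 = 10 | >5 to 11 | no | no |
| 11 mg prolonged-release once daily | 11 | >5 to 11 | no (11 is not >11) | yes |
| 10 mg twice daily | 2 × 10 = 20 | >15 to 20 | yes | yes |

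The excess for the second row is (11 − 10)/10 = 10%.

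**Step 2: mixed 8-week intervals.** With x of 56 days on the 11 mg tablet and the rest on 5 mg twice daily, ADD = (11x + 10(56 − x))/56.

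- x = 14: (154 + 420)/56 = 10.25 mg
- x = 28: (308 + 280)/56 = 10.5 mg
- x = 56: 616/56 = 11.0 mg

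All fall in the >5 to 11 mg band and none is flagged.

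**Step 3: which rule is the cause?** Separate RA from PsA and leave the rest unchanged. Both 10 and 11 mg remain in one band and below the flag, so the categorical table and the flag still show nothing. Only the continuous summary improves, because PsA values near 11 mg become visible. The flag and band are the main cause, and the pooling adds to it.

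**Step 4: period that the document supports.** The tablet was approved in December 2019 and Table 1 speaks as of June 2021. January 2020 to June 2021 is 18 months, and 18/81 = 22%. This is a rough measure, because ADD accrues over the follow-up year rather than at indexing.

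**Step 5: relative size of PsA in the pooled stratum.** German counts for 2017–2019 (Table 10) are RA 843 and PsA 169, a ratio of about 5 to 1; 169/(843 + 169) = 16.7%. These counts almost entirely predate the tablet, so they show only how far RA would dominate the pooled summary. The three indication counts sum to 843 + 169 + 190 = 1202, which is 91 above the stated total of 1111, so some patients appear to carry more than one code. If the total counts each patient once, includes only patients with one of the three codes, and all 91 are RA/PsA overlaps, then 91/169 = 54% of PsA-coded patients also carry an RA code. The true overlap is not given.

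**The case against.** The strongest reply is that nothing is contradicted. The defaults in Sections 9.1 and 9.7.1 allow exceptions, Sections 9.3.1 and 9.3.4 name the grouped form as an option, and the same grouping is used for several risk-factor analyses. This stands. A reader might infer that Section 9.7.1.2.1 breaches the protocol's default, but the documents do not support that. The pooling is a permitted option that suits this objective poorly, because the two indications have different approved regimens.

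A second reply is that separating the strata would not repair the categorical table. This also stands (Step 3), so the remedy cannot rest on un-pooling alone.

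Third, Section 9.9 concedes that ADD is imprecise, and the value assigned to an 11 mg tablet depends on a formula not yet written. A 1 mg/day contrast may be finer than the measure can resolve. This stands against tightening the ADD cut-off for PsA. It does not stand against counting dispensings of the formulation, which needs no ADD formula.

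Fourth, indication is a proxy taken from the diagnosis code nearest to index (Table 3, Section 9.9), so an RA patient properly taking the tablet could be classed as PsA. That risk is real and has to be shown alongside any PsA figure.

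Finally, the clinical stakes are small and the study is descriptive. This is accepted and reflected in the rating.

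**Conclusion.** The point holds as a minor one. As written, the ADD flag and bands count one 11 mg prolonged-release tablet daily as compliant in PsA, although the protocol caps PsA at 5 mg twice daily and lists that tablet for RA only. Pooling RA with PsA removes the one remaining summary that could have shown it.

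The size is 1 mg/day (10%), in Sweden and Germany only, with the number of patients unknown. The conclusion assumes that the SAP's formula gives the tablet its nominal 11 mg/day. A formula that did not distinguish the two regimens would not bring the PsA departure to light either.

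Two stronger readings should be avoided. A reader might take the whole period from January 2020 to December 2023 (48 of 81 months) as affected, but the protocol documents the PsA restriction only to June 2021, so 18 of 81 months is what it supports. A reader might also infer that overdosing outside UC goes undetected in general. It does not: 10 mg twice daily, the clinically larger case, is flagged.

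**What to change.** 1. In Section 9.7.1.2.1, report ADD for RA, PsA and UC separately.
2. Keep the >11 mg flag, and describe it as a tolerance for imprecise ADD.
3. Add one descriptive row to Table 3: the proportion of PsA patients with at least one dispensing of the 11 mg prolonged-release tablet on a date when that form was not approved for PsA. Tying the row to approval status on the dispensing date keeps it valid if the label changed later. Report it in Sweden, where Section 9.4.1 lists formulation in the drug register. Report it in Germany only if strength or product form is confirmed, since Section 9.4.4 names only the ATC code and dispensing date for prescriptions.
4. State that apparent PsA cases may be RA, and show the row again for PsA patients with no RA code in the baseline year.

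The cost is one phrase in Section 9.7.1.2.1, one Table 3 row with its repeat and a note, no new data in Sweden, and one question to the German data owner. The row is a small addition to the ADD-based measures. Cells will be small: at the protocol's minimum of 100 PsA patients, 5/100 has an exact 95% interval of 1.6% to 11.3%, and 0/100 has an upper limit of 3.6%. The repeat without RA codes will be smaller still.

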In May 2019, the EC requested a reassessment of the benefit-risk of tofacitinib pursuant to Article 20 of Regulation (EC) No 726/2004 due to a signal for increased risks of pulmonary embolism and mortality arising in an ongoing Pfizer-sponsored Phase 3b/4 safety study (A3921133) designed to evaluate the risk of malignancy and major adverse cardiac events in RA patients aged 50 years and older who had at least one cardiovascular (CV) risk factor. In November 2019, the Committee on Human Medicinal Products (CHMP) concluded, based on a recommendation from the Pharmacovigilance Risk Assessment Committee (PRAC), that patients treated with tofacitinib are at increased risk of venous thromboembolism (VTE) events, both for deep venous thrombosis as well as pulmonary embolism, especially in patients with risk factors for VTE. The PRAC further concluded that the risk of VTE events is dose-dependent. To minimise this risk, the PRAC recommended that warnings be added to the Summary of Product Characteristics (SmPC) regarding the increased risk of VTE observed in patients taking tofacitinib, especially for patients with known risk factors for VTE. The PRAC also recommended that treatment with tofacitinib be discontinued in patients with suspected VTE and that tofacitinib 10 mg BID for maintenance treatment is not recommended in patients with UC who have known VTE risk factors unless there is no suitable alternative treatment available. Clarifications on the posology were also added, particularly for UC patients in maintenance. Specifically, some patients (i.e., patients who failed to respond to alternative treatment options for UC such as tumour necrosis factor [TNF] inhibitor treatment) who had a reduction in response to 5 mg BID maintenance treatment may benefit from an increase in maintenance dose to 10 mg BID; for these patients, the presence of known risk factors for VTE should be considered. However, tofacitinib 10 mg BID for maintenance treatment should be used for the shortest duration possible.

The PRAC also concluded that, based on the interim analyses of Study A3921133, there is a potential increased risk of mortality. This was partly driven by an increased risk of serious infections among patients 65 years and older. As such, tofacitinib should be considered

among patients 65 years and older only if no suitable alternative treatment is available. These conclusions and revisions to the SmPC were approved by the EC on 31 January 2020.

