#### 9.3.3. Duration of tofacitinib therapy

Duration of tofacitinib therapy will be defined as the time from the date of the index tofacitinib dispensing to the date of discontinuation of tofacitinib. The operational definitions for duration of tofacitinib therapy will be further elaborated in the SAP and made specific to each database. For example, for NHIFA, the Hungarian administrative claims database, the following proxy will be used to estimate duration: time between two prescription dispensings of tofacitinib, allowing for a grace period of a pre-determined length (e.g., 90 days) before being considered to have discontinued tofacitinib. The length of the grace period will be determined during development of the SAP.

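### Table 3 defines a primary high-dose UC outcome by at least one prior biologic, although its label and Section 9.3.1 require none; a smaller gap is that time at high dose per UC patient is not tabulated

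*Protocol*

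**What the plan says.** Primary Objective 2 (Section 8) includes "Compliance to the recommended posology per indication (average daily dose [ADD]) and duration of use". Under it, Section 9.3.1 lists the proportion of patients with ADD of at least 15 mg in Weeks 16-23, 24-31, 32-39 and/or 40-47 "with evidence of a diagnosis for UC but no use of an alternative therapy", meaning a biologic, before tofacitinib.

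Section 9.3.1 refers to Table 3 (Section 9.3.2) for operational definitions, and Section 9.7.1.2.1 says that the posology outcomes listed in Table 3 are what will be tabulated. The Table 3 row carries the same label, with no prior alternative therapy. Its definition column asks for at least one UC code and at least one "prescription dispensing for a biologic (as identified by ATC codes) prior to and including the date of the index tofacitinib prescription".

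On duration, Section 9.3.3 defines the variable as "time from the date of the index tofacitinib dispensing to the date of discontinuation of tofacitinib", with no dose component. Section 9.7.1.2.1 adds: "Duration of tofacitinib therapy, as listed in Table 3 and defined in Section 9.3.3, will also be described, tabulated, and stratified by age". ADD is reported separately for each 8-week interval (Sections 9.3.4 and 9.7.1.2.1).

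The duration advice cited in Section 7 concerns the higher dose in UC: at first approval "10 mg BID for induction (up to a 16-week period) and 5 mg BID for maintenance", and after the Article 20 referral "tofacitinib 10 mg BID for maintenance treatment should be used for the shortest duration possible".

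**The concern.** The outcome is meant to find UC patients kept on a high dose after Week 15 without having tried a biologic. Section 7 describes 10 mg BID maintenance as an option for patients who lost response on 5 mg BID and had failed alternatives such as TNF inhibitors. Requiring a biologic turns the outcome round: it counts the group in which the higher dose may be right and leaves out the group in which it is questionable. A programmer who follows Table 3, as the analysis section directs, would report the opposite population under the intended label.

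The secondary matter is time at the higher dose. A few patients kept on 10 mg BID for most of Weeks 16-47 and many patients given one short spell mean different things for advice to keep that dose as short as possible. Total treatment time at any dose does not separate them. Nor do separate interval summaries when the spells are spread over the period.

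**Working it through.** The plan gives no figure for this point, so there is none to reproduce.

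**1. The biologic condition, place by place**

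- Section 9.3.1, UC with ADD of at least 15 mg: no biologic before initiation; no look-back stated.
- Table 3, same outcome, label: no biologic before initiation.
- Table 3, same outcome, definition: at least one biologic, up to and including the index date; no look-back stated.
- Table 3, UC with a VTE risk factor and ADD above 10 mg: 0 biologics in the 12 months before and including the index date.

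Three of the four agree on none. The definition column of the outcome at issue is the exception.

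**2. What the literal definition would count**

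Let N be the number of UC patients, b the share with a prior biologic, and h1 and h0 the shares ever at high dose with and without one.

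- Intended count: N(1 - b)h0. Literal count: N b h1. No patient is in both.
- The ratio is b h1 / [(1 - b)h0]. The documents give none of b, h1 or h0, so neither the size nor the direction of the error is known.
- Illustration: Table 10 gives 190 German UC patients. With b = 0.5 (assumed), 95 have a prior biologic. With h1 = 0.230, 0.314 or 0.464 (from the assumed model in step 4), the literal count is 95 x h1 = 21.8, 29.8 or 44.1. About 22 to 44 patients would be reported, none of whom fits the label.

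**3. What interval shares reveal about time at high dose**

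For shares p1 to p4 in the four intervals of Weeks 16-47, the ever-high proportion lies between max(p) and min(1, sum of p). Mean high-dose intervals per user is the sum of p divided by that proportion. All shares below are assumptions.

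- 20/20/20/20%: 0.8/0.8 = 1.0 to 0.8/0.2 = 4.0.
- 40/20/10/10%: 0.8/0.8 = 1.0 to 0.8/0.4 = 2.0.
- 80/0/0/0%: 0.8/0.8 = 1.0 exactly, so nothing is hidden.

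A constructed example shows the same. Take 100 UC patients with a prior biologic, all treated throughout, at 20 or 10 mg per day. In one cohort the same 25 are high in all four intervals; in the other a different 25 are high in each. Every interval shows 75 and 25 patients in the two dose categories, mean 12.5 mg and SD 4.35, and total duration is identical. Yet high-dose time is 32 weeks for each of 25 users in one, and 8 weeks for each of 100 users in the other.

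**4. Where in the range, for flat 20% shares**

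Two-state chain: r is the chance of staying high from one interval to the next, entry q = 0.2(1 - r)/0.8, and P(any) = 1 - 0.8(1 - q)^3.

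- r = 0.5: P(any) = 0.464; 0.8/0.464 = 1.72 intervals per user; high in all four 0.2r^3/P(any) = 5%.
- r = 0.8: P(any) = 0.314; 2.55 per user; 33%.
- r = 0.95: P(any) = 0.230; 3.48 per user; 75%.

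**5. How the two points interact**

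Table 3 read literally would, if the four intervals are joined as any-of-four, give an ever-high proportion for patients with a prior biologic. Their mean number of high-dose intervals could then be derived, but not its spread: a mean of 2.0 fits every user at 2, or two thirds at 1 and one third at 4, since (2/3) x 1 + (1/3) x 4 = 2. Correcting Table 3 removes even this, so the count has to be tabulated if it is wanted.

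**The case against.** On Table 3, the sponsor can say that this is an evident slip: label and outcome list agree, Section 9.3.2 calls the algorithms preliminary, and the SAP will refine them. That stands as far as it goes. A reader might infer that the study will report the wrong population; the documents do not show that, because the SAP is not at hand and may have it right. But the definition column is the text that the analysis section points to, and it is wrong as written.

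On duration, the objection is stronger. A reader might infer that the plan cannot assess duration of use and so fails part of a primary objective. The documents do not support that:

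- The one numeric limit cited, induction of up to 16 weeks, falls on an interval boundary, so high dose after it is visible in the ADD tables, which are also split by prior biologic.
- Advice to use the shortest possible duration has no threshold, and Section 9.9 already says that guidance left to clinical discretion can be assessed only to a limited extent.
- Restricting the compliance outcome to patients without a prior biologic fits the recommendation.
- Sections 9.3.3 and 9.3.4 leave operational detail on duration and ADD to the SAP, which could add such a table.
- The and/or wording in Section 9.3.1 does not settle whether the four intervals are joined.

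What remains is narrow. Separate interval shares do not determine time at high dose per user, and Section 9.9, which admits imprecise ADD and undetectable re-induction, does not mention this.

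**Conclusion.** The Table 3 definition contradicts its own label and Section 9.3.1, and should be corrected whatever is decided about duration. Taken literally, it replaces the intended patients entirely with others. This rests on the text alone and needs no assumption; only the illustrative 22 to 44 patients do.

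The duration point is a minor descriptive gap. It applies to Sweden and Germany, the two countries where ADD is assessed, to UC patients with a prior biologic, and to high-dose spells spread over Weeks 16-47. With flat 20% shares the uncertainty is fourfold (1.0 to 4.0 intervals per user); with falling shares it is smaller, and with spells confined to one interval it disappears. The shares, persistence values and the 50% biologic share are all assumptions. No number in the protocol is wrong on this account.

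**What to change.** **Table 3.** Change the definition to at least one UC code and 0 biologic dispensings in the 12 months prior to and including the index date, and state the same look-back in Section 9.3.1. Describe the group as having no biologic recorded in 12 months, not as biologic-naive: earlier use is not seen, and Swedish capture of hospital-administered biologics is incomplete (Section 9.9). The cost is one line of text.

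**Optional addition.** For Sweden and Germany, add one table of the number (0 to 4) of Weeks 16-47 intervals with ADD of at least 15 mg per UC patient, by biologic use in the prior 12 months. It uses ADD values already computed. Label it descriptive and coarse, not a compliance measure, for these reasons:

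- With w weeks at 10 mg BID and the rest of the interval at 5 mg BID, ADD = 10 + 10w/8. At w = 4 this is 15.0 mg; at w = 3.5 it is 14.4 mg, so a 7-week spell split evenly over two intervals counts as 0. Table 3 notes a similar miss: "This definition will miss those who have 1 10-mg BID prescription and the remaining prescriptions are 5-mg BID".
- For one unbroken spell, counts 0 to 4 correspond to under 8, 4 to under 16, 8 to under 24, 16 to under 28, and 24 to 32 weeks. Adjacent counts overlap; counts two or more apart do not.
- Re-induction cannot be told apart from maintenance (Section 9.9).
- Numbers may be small. The 30 or 22 German high-dose users in the illustration (r = 0.8 or 0.95) give 1.96 x sqrt(0.25/n) = 17.9 or 20.9 points either side of a 50% share. The base of 190 dates from 2017-2019 while indexing runs to the end of 2023, so the final cohort may be larger.
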